3.3.1 Inclusion Criteria

To be considered eligible to participate in this study, a subject must meet the inclusion criteria listed below:

- 1. Male or female between 18 and 75 years of age.
- 2. Clinical diagnosis of NASH with at least stage F1 fibrosis as evident by:
 - Liver fat content ≥10% as assessed by MRI-PDFF and a corrected T1 (cT1) of ≥830 msec as assessed by multiparametric MRI.
- 3. Aspartate aminotransferase ≥20 U/L.
- 4. Clinically documented diagnosis of T2DM ≥6 months prior to randomization.
- 5. If on a T2DM medication regimen, specifically thiazolidinediones, glucagon-like peptide-1 (GLP-1) agonists, dipeptidyl peptidase-4 (DPP-4) inhibitors, or sodium-glucose cotransporter-2 (SGLT-2) inhibitors, must be maintained on a stable dose regimen for ≥90 days prior to randomization.
- 6. If on vitamin E, must be maintained on a stable dose of ≤400 IU for ≥90 days prior to randomization with no anticipated dose increases during the study.
- 7. Regimens for other permitted concomitant medications, as described in Section 4.5 of the protocol, must be stable for ≥28 days prior to randomization.
- 8. Body mass index (BMI) >25 kg/m².
- 9. Females of child-bearing potential (FOCP) and males participating in the study must either agree to use at least 2 approved barrier methods of contraception or be completely abstinent from sexual intercourse, if this is their usual and preferred lifestyle, throughout the duration of the study and for at least 90 days after the last

dose of study drug. Females who are postmenopausal must have appropriate supporting documentation with a corresponding follicle-stimulating hormone (FSH) test result to support status.

10. Ability to understand and sign a written ICF.

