An absolute change in LFC of 5% as measured by magnetic resonance imaging-estimated proton density fat fraction (MRI-PDFF) has been reported to be the minimal clinically significant difference between active treatment and placebo that correlates with histological improvement in NASH (Loomba et al., 2015, Patel et al., 2015). Furthermore, Harrison and colleagues reported a pooled standard deviation of 6.3% for changes from Baseline in LFC (Harrison et al., 2018). Based on this standard deviation, 35 subjects in each treatment group will provide 90% power to show a difference of 5 percentage points between any 2 treatment groups at the 5% level of significance. To allow for a dropout rate of 10%, 39 subjects will be randomized to each of the 3 treatment groups. Due to the exploratory nature of this study, enrollment may be stopped early when sufficient information has been gathered to evaluate the effects of HTD1801 on LFC.

An interim analysis will be conducted after a minimum of 51 subjects complete the assessment of the primary efficacy endpoint to assess sample size assumptions and futility through conditional power.

3.2. **RANDOMIZATION AND MASKING**

This is a multicenter, randomized, double-blind study. Subjects will be centrally randomized via an interactive web response system (IWRS) in a 1:1:1 ratio to one of 3 groups:

HTD1801 500 mg BID

HTD1801 1000 mg BID

Placebo BID

In addition to the subject ID number, subjects will be assigned a randomization number, as well as a kit ID number corresponding to a pre-packaged and numbered study drug kit. The randomization schedule was prepared by a non-study statistician using PharPoint standard operating procedure BIO002.

All subjects and study personnel, except for the unblinded statistician, the IWRS vendor and the study drug packaging supplier, will remain blinded to the treatment administered throughout the study. All study drugs will be provided in matching white tablets, 4 tablets to a pouch, 2 pouches to be administered each day.

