3.3.4. Missing Data and Outliers

Every effort will be made to obtain required data at each scheduled evaluation from all subjects who have been treated. For subjects who do not complete the 18-week evaluation, endpoints that will only be measured at Week 18 or the Early Termination (ET) visit (i.e., LFC, HOMA-IR, Pro-C3, ELF) will have the value at the ET visit carried forward for the missing Week 18 visit.

For all non-LFC secondary endpoints measured at at least one post-baseline timepoint other than Week 18/ET, missing Week 18 values will be imputed using a multiple imputation procedure for all subjects with an available measurement prior to Week 18. Multiple imputation relies on the assumption that the data are missing at random. This method of imputation produces unbiased estimators of the mean and standard error, and, as such, is preferred over single imputation methods. For this method, the procedure requires production of multiple datasets containing plausible values for each missing value. These plausible values are generated using available auxiliary information (site, treatment, baseline assessment value, baseline LFC, and baseline ALT).

Using a set of values rather than a single value better accounts for the uncertainty about the value being imputed. For this imputation, the Markov chain method will be used. SAS PROC MI will be used to generate 10 possible imputed datasets.

For each variable that has imputations performed, the following steps will be followed:

1. Missing values will be imputed using PROC MI. This will result in 10 datasets per variable.
2. Efficacy endpoints will be derived from the appropriate set of 10 datasets produced by PROC MI using the imputed values.
3. Each efficacy endpoint will be analysed 10 times (once per source dataset) using the appropriate statistical model for that endpoint.
4. For each endpoint, the results from the analysis from each of the 10 datasets will be combined using PROC MIANALYZE to produce an inferential result for the parameter of interest.

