5. STATISTICAL METHODS

Descriptive statistical methods will be used to summarize the data from this study, with hypothesis testing performed for the primary and other selected efficacy endpoints. Unless stated otherwise, the term “descriptive statistics” refers to number of subjects (n), mean, median, standard deviation (SD), minimum and maximum for continuous data and frequencies and percentages for categorical data. Additional statistical methods include analysis of covariance (ANCOVA) and logistic regression. All data collected during the study will be included in data listings. Unless otherwise noted, the data will be sorted first by treatment group, subject number, and then by date within each subject number.

The term ‘treatment group’ refers to all subjects on the same dosing regimen. There will be three treatment groups in this study:

HTD1801 500 mg BID

HTD1801 1000 mg BID

Placebo BID

All statistical tests will be two-sided with an alpha level of 0.05.

The statistical analyses will be conducted with the SAS[®] System version 9.4 or higher. All analyses will be subject to formal verification procedures. Specifically, results will be verified utilizing independent programming prior to issuance of the draft statistical report. All documents will be verified by the lead statistician to ensure accuracy and consistency of analyses.

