5.2.5. Secondary Efficacy Analysis

Change and percent change from Baseline in LFC will be summarized by treatment group and study visit. Differences in percent change from Baseline in LFC will be assessed by analysis of covariance that includes the effects of treatment group, Baseline LFC, and Baseline ALT, comparing each active treatment group to placebo, as well as a comparison of the combined active treatment groups vs. placebo. A figure summarizing LS means of percent change from Baseline at Week 18 by treatment group will also be generated.

Changes from Baseline to Week 18 in the laboratory assessments listed as secondary efficacy endpoints (fasting glucose, HbA1c, HOMA-IR, LDL-c, serum triglycerides, HDL-c, AST, ALT,

Pro-C3, ELF, total bile acids, C4, FGF19) will be assessed by analysis of covariance that includes the effects of treatment group and Baseline value, comparing each active treatment group to placebo. For these analyses, missing Week 18 values will be imputed using the methods described in section 3.3.4. For HbA1c, this model will also be run without imputed values. For all bile acid analyses other than total bile acid, all analyses will be performed without imputation. Figures summarizing change from Baseline over time by treatment group will also be generated for these laboratory assessments. The number and percentage of subjects who achieve $\geq 30\%$ relative reduction in LFC as measured by MRI-PDFF from Baseline to Week 18 will be summarized by treatment group and study visit. The proportion of subjects who achieve $\geq 30\%$ relative reduction in LFC as measured by MRI-PDFF from Baseline to Week 18 will be analyzed by logistic regression that includes the effects of treatment group, Baseline LFC, and Baseline ALT. A figure summarizing the proportion of subjects achieving $\geq 30\%$ relative reduction in LFC as measured by MRI-PDFF from Baseline to Week 18 by treatment group will also be generated.

The number and percentage of subjects who normalize LFC to $< 5\%$ as measured by MRI-PDFF at Week 18 will be summarized by treatment group and study visit. The proportion of subjects who normalize LFC to $< 5\%$ as measured by MRI-PDFF at Week 18 will be analyzed by logistic regression that includes the effects of treatment group, Baseline LFC, and Baseline ALT. A figure summarizing the proportion of subjects who normalize LFC to $< 5\%$ at Week 18 by treatment group will also be generated.

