The number and percentage of subjects who achieve $\geq 5\%$ absolute reduction in LFC as measured by MRI-PDFF from Baseline to Week 18 will be summarized by treatment group and study visit. The proportion of subjects who achieve $\geq 5\%$ absolute reduction in LFC as measured by MRI-PDFF from Baseline to Week 18 will be analyzed by logistic regression that includes the effects of treatment group, Baseline LFC, and Baseline ALT. A figure summarizing the proportion of subjects who achieve $\geq 5\%$ absolute reduction in LFC from Baseline to Week 18 by treatment group will also be generated.

The number and percentage of subjects with elevated ALT at Baseline who normalize ALT at Week 18 will be summarized by treatment group and study visit. The proportion subjects of with elevated ALT at Baseline who normalize ALT at Week 18 will be analyzed by logistic regression that includes the effects of treatment group, Baseline LFC, and Baseline ALT. A figure summarizing the proportion of subjects who normalize ALT at Week 18 by treatment group will also be generated. For this analysis, missing Week 18 values will be imputed using the multiple imputation method as described in section 3.3.4.

If the data is not amenable to analysis by logistic regression for any of the responder endpoints included in this section, then comparisons between treatment groups may be performed using Cochran-Mantel Haenszel (CMH) testing instead.

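### The sparse responder endpoints, chiefly LFC <5%, have no prespecified analysis that survives an arm with no responders; the CMH fallback is optional and undefined

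*SAP*

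**What the plan says.** SAP 5.2.5 states a model for four responder endpoints: ≥30% relative LFC reduction, ≥5-point absolute LFC reduction, LFC below 5%, and ALT normalization among subjects with elevated Baseline ALT. Each "will be analyzed by logistic regression that includes the effects of treatment group, Baseline LFC, and Baseline ALT". No estimation method or test statistic is named, so ordinary maximum likelihood (ML) is the natural reading, though it is not written down.

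The section closes with a fallback. "If the data is not amenable to analysis by logistic regression for any of the responder endpoints included in this section", treatment comparisons may be made by CMH testing. The SAP does not say what counts as failure, which strata apply, which effect measure is reported, or how the result is pooled. Protocol 9.2.3.2 gives the same logistic model for the three LFC endpoints and no fallback.

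Only ALT normalization is multiply imputed. Under step 4 of SAP 3.3.4, "the results from the analysis from each of the 10 datasets will be combined using PROC MIANALYZE". For LFC the ET value is carried forward, so those endpoints have one dataset each. Protocol 3.3.1 requires "Liver fat content ≥10% as assessed by MRI-PDFF" at entry.

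**The concern.** A subject entering at 10% or more must lose over 5 points of LFC to fall below 5%, so few placebo subjects may do so. If none does, the ML log odds ratio for each dose against placebo diverges and the Wald test tells the reader nothing, however many active-arm subjects respond. That is the outcome most favourable to the drug.

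The SAP foresees trouble but leaves the response open. An unstratified CMH test gives a p-value without adjustment for Baseline LFC or ALT, and no finite odds ratio when a cell is empty. Because the switch is optional and its trigger undefined, the method could be chosen after the counts are known. For ALT normalization, a raw CMH chi-square supplies no estimate and standard error for step 4, and nothing is said about what happens if only some of the 10 imputed datasets fail.

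**Working it through.** **The plan's own figure.** SAP 3.1 gives a difference of 5 points, a "pooled standard deviation of 6.3% for changes from Baseline in LFC", 90% power and two-sided 5% alpha. The normal quantiles 1.960 and 1.282 sum to 3.242, and n = 2 × 3.242² × 6.3² / 5² = 33.4, so 34 by the normal approximation. The t-test needs 34.35, so 35, with 90.5% power. 35 / 0.9 = 38.9, so 39 per arm and 117 in all. The stated size is reproduced. No rate, power or size is given for any responder endpoint.

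**Chance of no placebo responder.** P(zero) = (1 − p)^n. The rate p is not in the documents. I derived a range from the plan's SD of 6.3, assuming a normal change independent of baseline, a placebo mean change of 0 to −2 points, and a normal Baseline LFC cut off at 10% (mean/SD before cutting 16/5, 18/6 and 20/7).

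| Endpoint | Implied placebo rate | P(zero), n = 35 |
|---|---|---|
| LFC <5% | 2.8-8.8% | 37% to 4% |
| ≥30% reduction | 17-31% | at most 0.2% |
| ≥5-point reduction | 21-32% | at most 0.02% |

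For LFC <5%: 0.972^35 = 0.37 and 0.912^35 = 0.04. SAP 3.1 allows enrollment to stop early. At an assumed 17 per arm (51/3) the same rates give 0.972^17 = 0.62 and 0.912^17 = 0.21.

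For ALT normalization neither subset size nor rate is given. With an assumed 20 elevated-ALT placebo subjects, P(zero) is 36% at a 5% rate, 12% at 10% and 1.2% at 20%.

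**What the available tests give for 0/35 v 5/35 (unadjusted).**
- Likelihood ratio: 2 × [5 ln(5/2.5) + 30 ln(30/32.5) + 35 ln(35/32.5)] = 7.32, p = 0.007.
- CMH: expected 2.5, variance 35 × 35 × 5 × 65 / (70² × 69) = 1.178, chi-square 2.5² / 1.178 = 5.31, p = 0.021.
- Fisher exact: p = 0.054.
- ML Wald: unusable.

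The results lie on both sides of 0.05.

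**What Firth gives for 0/35 v 6/35 (no covariates).** In a 2×2 table it amounts to adding 0.5 to each cell: the odds are 6.5/29.5 = 0.220 and 0.5/35.5 = 0.0141, with ratio 15.6. The penalised likelihood-ratio p is 0.010, with a profile-likelihood 95% CI of about 1.7 to 2,070: wide, but a usable lower bound. CMH gives p = 0.011 and Fisher 0.025. Firth's estimate over its standard error, 2.75 divided by 1.51, is 1.82, p = 0.069, which matters for pooling.

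**Bias of ML and Firth.** The SAP model was simulated with 1,500 runs per case, 35 per arm and assumed covariate effects of 0.5 and 0.3 log-odds per SD.

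| Rates | True OR | ML (finite runs) | Firth |
|---|---|---|---|
| 20% v 50% | 4.41 | 4.78 (+8%) | 4.34 (−2%) |
| 10% v 40% | 6.63 | 7.62 (+15%) | 6.67 (+1%) |
| 20% v 20% | 1.00 | 0.99 | 0.99 |
| 2% v 13% | 7.63 | 3.88; no finite OR in 52% of runs | 5.89 (−23%) |

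**Pooling.** In a 10-imputation example, the Mantel-Haenszel log odds ratio with its standard error, pooled by Rubin's rules, gave p = 0.110. A Wilson-Hilferty transform of the CMH statistic gave p = 0.104.

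**The case against.** The strongest reply is that the SAP already anticipates failure and names an alternative, and that using it costs no power. This stands. With assumed rates of 3%, 8% and 15% and 35 per arm, always using CMH on separation rejected in 40.1% of simulated trials and Firth in 40.8%. Other simulated comparisons gave Firth 40% v CMH 45%, and 68.5% v 68.8%. A case for Firth on power would have to compare it with a Wald test kept after separation, which the SAP does not require.

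A reader might also infer more than the documents support:
- *That all four endpoints are at risk.* On the plan's own SD, separation is negligible for the ≥30% and ≥5-point endpoints.
- *That CMH cannot be pooled or must lose the covariates.* It can be pooled, as shown above, and categorized baseline values could serve as strata. The gap is that the SAP specifies neither. With an empty arm, the Mantel-Haenszel log odds ratio is not finite either.
- *That ML odds ratios are badly inflated.* The excess is 8-15% at 35 per arm in the common-responder cases and absent under no effect, so no false positives are shown. In very sparse data the finite ML estimates are too low.

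It is also fair that the SAP names no Wald test, that Firth is itself logistic regression, that counts and percentages by arm are reported regardless, and that these are secondary endpoints of a proof-of-concept study without multiplicity adjustment.

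None of this supplies the missing trigger, strata, effect measure or pooling rule.

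**Conclusion.** The concern holds for LFC <5% and possibly for ALT normalization. An empty placebo arm has roughly a 4-37% chance at 35 per arm for LFC <5%, and more if enrollment stops early. The stated model then yields no usable odds ratio or Wald test, and the undefined fallback leaves open a choice that can move p across 0.05. It does not extend to a general failure of the responder analyses, and the primary ANCOVA is untouched.

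The percentages rest on assumed baseline distributions, placebo changes and covariate effects. The ALT subset cannot be sized from the documents. What does not depend on these assumptions is that the fallback is discretionary and incomplete. This is a cheap improvement to secondary analyses, worth making before unblinding.

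**What to change.** In SAP 5.2.5:

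1. For LFC <5% and ALT normalization, prespecify Firth penalised-likelihood logistic regression with treatment, Baseline LFC and Baseline ALT. For LFC <5%, report the penalised-likelihood-ratio test and profile-likelihood 95% CI; ALT normalization uses the same method, with pooled inference as in item 4.
2. For the ≥30% and ≥5-point endpoints, keep the present model, with the same Firth analysis as the mandatory fallback if any arm has zero or all responders or the fit does not converge.
3. Delete the discretionary CMH sentence.
4. For imputed ALT normalization, apply Firth to all 10 datasets, pool estimates and standard errors through PROC MIANALYZE, and state that the pooled inference is Wald-type and conservative in sparse data. Profile limits and likelihood-ratio tests do not pass through that step (compare p = 0.069 with 0.010 above).

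The cost is SAP text and an option in PROC LOGISTIC, with no new data or subjects. The Protocol's covariates and logistic model are kept. The downsides are that Firth shrinks estimates in very sparse data (true odds ratio 7.63, estimate 5.89) and is less familiar to clinical readers.

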5.3. SAFETY

5.3.1. Adverse Events

AEs will be mapped to a Medical Dictionary for Regulatory Activities (MedDRA) version 20.1 preferred term (PT) and system organ classification (SOC). If a subject experiences multiple events that map to a single preferred term, the greatest severity grade according to the Common Terminology Criteria for Adverse Events (CTCAE) Version 4.0, and strongest investigator assessment of relation to study medication will be assigned to the preferred term for the appropriate summaries. Should an event have a missing severity or relationship, it will be classified as having the highest severity and/or strongest relationship to study medication. The occurrence of TEAEs will be summarized by treatment group by SOC, PT, and severity. Separate summaries of treatment-emergent serious adverse events (SAEs), TEAEs related to study drug, severe or life-threatening TEAEs, and TEAEs leading to the discontinuation of study treatment will be generated. Additionally, the occurrence of liver-specific AEs will be summarized by treatment group. All adverse events reported will be listed for individual subjects showing verbatim term, PT and SOC. All AEs that occurred prior to the initiation of study treatment will be excluded from the tables but will be included in the listings.

Missing onset dates will be imputed as previously outlined in Section 3.3.5 as required to determine treatment-emergent events.

5.3.2. Clinical Laboratory Assessments, Vital Signs, Height, and Weight

Descriptive summaries of selected (quantitative) clinical laboratory results, and change from Baseline will be presented by time point and treatment group. Laboratory abnormalities will also be summarized by treatment group. Shift tables (low, normal, high) for change from Baseline to Week 18, or last available study visit, will be presented for all appropriate clinical laboratory parameters. Additionally, shift tables (normal, abnormal) for change from Baseline to Week 18, or last available study visit, will be presented for the clinical laboratory parameters listed below. Laboratory abnormalities will be determined using the following criteria:

Laboratory Parameter	Clinically Significant Abnormal Criteria
ALP	> 348 U/L
ALT	> 123 U/L
AST	> 102 U/L
Direct Bilirubin	> 0.20 mg/dL
Total Bilirubin	> 2.00 mg/dL

GGT	> 156 U/L in Males > 114 U/L in Females
Glucose	< 60 mg/dL
INR	≥ 1.3
HbA1c	≥ 9.5%

Additionally, descriptive summaries and change from Baseline in weight will be presented by timepoint and treatment group.

Values for all safety variables will be listed by subject and visit (as applicable).

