3.3.2 Exclusion Criteria

To be eligible for entry into the study, the subject must not meet any of the exclusion criteria listed below:

- 1. Clinically significant acute or chronic liver disease unrelated to NASH, including but not limited to primary sclerosing cholangitis (PSC), Wilson's disease, alpha-1 antitrypsin (AAT) deficiency (MZ or ZZ phenotype), hepatitis B or C, hereditary hemochromatosis, alcoholic liver disease, and drug induced liver disease.
- 2. Clinically or histologically documented cirrhosis.
- 3. Poorly controlled T2DM (HbA1c ≥9.5%) or Type 1 Diabetes Mellitus.
- 4. Hepatitis B surface antigen positive.
- 5. Hepatitis C antibody positive with active infection.
- 6. Human immunodeficiency virus (HIV)-1 or HIV-2 infection.
- 7. Glucose-6-phosphate dehydrogenase (G6PD) deficiency.
- 8. Any prior history of hepatic decompensation (encephalopathy, ascites, gastroesophageal varices, hepatorenal syndrome), platelet count <150,000/mm³, international normalized ratio (INR) ≥1.3 despite vitamin K supplementation, serum albumin <3.2 g/dL, or a prior or planned liver transplantation.
- 9. History of alcohol or substance abuse or dependence.
- 10. Hepatic steatosis that, in the opinion of the Investigator, is primarily related to alcohol consumption.
- 11. Inability to undergo MRI for any reason.

Note: Mild sedative use (if not prohibited as described in Section 4.6 of the protocol) for MRI procedures is permitted.

- 12. Laboratory parameters within any of the following ranges:
 - AST >5 × ULN.
 - ALT ≥5 × ULN.
 - Estimated glomerular filtration rate (eGFR) <60 mL/min/1.73 m².
 - Hemoglobin <11 g/dL for males or females.
 - Direct bilirubin <LLN or >ULN.
 - Total bilirubin <LLN or >ULN.

Note: Total bilirubin >ULN due to Gilbert's syndrome is acceptable provided that direct bilirubin, reticulocyte count, and hemoglobin are within the laboratory defined normal ranges.

• Thyroid-stimulating hormone (TSH) <LLN or >1.5 \times ULN.

Note: Subjects on a medication for a thyroid abnormality may enroll provided that they have been maintained on a stable dose for ≥ 90 days prior to randomization.

- 13. Current use of oral prednisone/prednisolone (or prednisone/prednisolone equivalent) >10 mg/day.
- 14. History of myocardial infarction, congestive heart failure, uncontrolled cardiac arrhythmia, unstable angina, coronary bypass surgery, or percutaneous coronary intervention ≤12 months prior to Screening.

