7.9 LIVER ADVERSE EVENTS

The algorithm (Chalasani and Regev 2016) described in Table 8 will be used to monitor for drug-induced liver injury (DILI).

Table 8. Algorithm to Monitor for DILI

| Treatment Emergent ALT | Treatment Emergent Total Bilirubin (TB) | Liver Symptoms | Actions |
|--|--|----------------|---|
| Normal Baseline: ALT >2x ULN | Normal | None | Repeat ALT, AST, ALP, TB, in 2-5 days after receipt of the scheduled ALT results (Table 1). |
| Elevated Baseline: ALT >2x Baseline or >300 U/L (whichever occurs first) | Patients with Gilbert's syndrome: No change in Baseline TB | None | Follow up for symptoms. |

| Treatment Emergent ALT | Treatment Emergent Total Bilirubin (TB) | Liver Symptoms | Actions |
|---|--|---|---|
| Normal Baseline: ALT >5x ULN | Normal | None | Interrupt study drug. Initiate close monitoring and workup for competing etiologies. |
| Elevated Baseline: ALT >5x Baseline or >500 U/L (whichever occurs first) | Patients with Gilbert's syndrome: No change in Baseline TB | | Study drug can be restarted only if another etiology is identified and liver enzymes return to baseline. |
| Normal Baseline: ALT >2x ULN | TB >2x ULN | None | Interrupt study drug. Initiate close monitoring and workup for competing |
| Elevated Baseline: ALT >2x Baseline or >300 U/L (whichever occurs first) | Patients with Gilbert's syndrome: Doubling of direct bilirubin | | etiologies. Study drug can be restarted only if another etiology is identified and liver enzymes return to baseline. |
| Normal Baseline: ALT >2x ULN | Normal or elevated | Severe fatigue, nausea, vomiting, right upper quadrant pain | Interrupt study drug. Initiate close monitoring and workup for competing |
| Elevated Baseline: ALT >2x baseline or >300 U/L (whichever occurs first) | - | | etiologies. • Study drug can be restarted only if another etiology is identified and liver enzymes return to baseline. |

Note: Baseline is the average of the Screening and Baseline visit ALT measurements.

As described in Table 8, close monitoring of the subject must be initiated if certain signals of a possible DILI are detected. At a minimum, close monitoring includes:

- Repeating liver enzyme and serum bilirubin tests 2-3 times weekly. The frequency of retesting can decrease to once a week or less if abnormalities stabilize or if the study drug has been discontinued and the subject is asymptomatic.
- Obtaining a more detailed history of the subject's symptoms and prior or concurrent diseases.

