- 14.3.1.4 Treatment-Emergent Serious Adverse Events by System Organ Class and Preferred Term – Safety Set
- 14.3.1.5 Treatment-Emergent Adverse Events Leading to the Discontinuation of Study by System Organ Class and Preferred Term – Safety Set
- 14.3.4.1 Clinical Laboratory Chemistry Parameters by Time Point – Safety Set
- 14.3.4.2 Clinical Laboratory Hematology Parameters by Time Point – Safety Set
- 14.3.4.3 Clinical Laboratory Urinalysis Parameters by Time Point – Safety Set
- 14.3.4.4 Clinical Laboratory Abnormalities – Safety Set
- 14.3.4.5 Clinical Laboratory Parameter Shifts from Baseline to Week 18 – Safety Set
- 14.3.4.6 Clinical Laboratory Parameter Shifts to Abnormal from Baseline to Week 18 – Safety Set
- 14.3.5.1 Vital Signs by Study Visit – Safety Set
- 14.3.5.2 12-Lead ECG Assessments by Study Visit – Safety Set

Summary Figures

Efficacy

- 14.2.1.3 Bar Plot of Mean Absolute Change from Baseline at Week 18 in LFC
- 14.2.1.4 Bar Plot of Mean Percent Change from Baseline at Week 18 in LFC
- 14.2.1.5 Bar Plot of Proportion of Subjects with $\geq 30\%$ Reduction in LFC from Baseline to Week 18
- 14.2.1.6 Bar Plot of Proportion of Subjects who normalize LFC to $< 5\%$ at Week 18
- 14.2.1.7 Bar Plot of Proportion of Subjects who achieve $\geq 5\%$ absolute reduction in LFC from Baseline to Week 18
- 14.2.3.1 Bar Plot of Mean Change from Baseline by Time Point in Fasting Glucose
- 14.2.3.2 Bar Plot of Mean Change from Baseline by Time Point in HbA1c
- 14.2.3.3 Bar Plot of Mean Change from Baseline by Time Point in HOMA-IR
- 14.2.3.4 Bar Plot of Mean Change from Baseline by Time Point in AST
- 14.2.3.5 Bar Plot of Mean Change from Baseline by Time Point in ALT
- 14.2.3.6 Bar Plot of Proportion of Subjects who Normalize ALT at Week 18
- 14.2.3.7 Bar Plot of Mean Change from Baseline by Time Point in Lipids
- 14.2.3.8 Bar Plot of Mean Change from Baseline by Time Point in Pro-C3
- 14.2.3.9 Bar Plot of Mean Change from Baseline by Time Point in ELF
- 14.2.3.10 Bar Plot of Mean Change from Baseline by Time Point in Total Bile Acids
- 14.2.3.11 Bar Plot of Mean Change from Baseline by Time Point in C4
- 14.2.3.12 Bar Plot of Mean Change from Baseline by Time Point in FGF19

Data Listings

- 16.2.1.1 Subject Disposition
- 16.2.1.2 Informed Consent

- 16.2.2.1 Protocol Deviations/Violations
- 16.2.2.2 Inclusion/Exclusion Criteria
- 16.2.3 Reasons for Exclusion from Analysis Sets
- 16.2.4.1 Demographics
- 16.2.4.2 Medical History

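### The SAP's fixed liver-test limits have no Baseline term, so the abnormality summary can count subjects already above a limit at entry, and some rises that meet the protocol's 2x ALT triggers show no shift

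*SAP*

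**What the plan says.** SAP 5.3.2 introduces its limits with "Laboratory abnormalities will be determined using the following criteria". The limits are absolute: ALT above 123, AST above 102, ALP above 348, GGT above 156 (men) or 114 (women) U/L, total bilirubin above 2.00 mg/dL, and others. None is a multiple of Baseline.

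The same section plans a summary of abnormalities by arm and two kinds of shift table. One is low/normal/high. The other uses the limits above: "shift tables (normal, abnormal) for change from Baseline to Week 18, or last available study visit, will be presented". SAP Section 10 lists the abnormality summary as Table 14.3.4.4, titled "Clinical Laboratory Abnormalities – Safety Set", with no statement that it is restricted to post-dose or treatment-emergent values.

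Protocol 3.3.2, criterion 12, excludes ALT at or above 5 x ULN and AST above 5 x ULN, so raised transaminases below those levels are eligible. Bilirubin is tighter: "Total bilirubin <LLN or >ULN" is excluded, apart from Gilbert's syndrome.

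Protocol 7.9, Table 8, sets the ALT triggers used to monitor for drug-induced liver injury:
- Lower level: "Normal Baseline: ALT >2x ULN", or "Elevated Baseline: ALT >2x Baseline or >300 U/L (whichever occurs first". This level appears alone, with raised bilirubin, and with symptoms.
- Higher level: "Normal Baseline: ALT >5x ULN", with a corresponding rule for an elevated Baseline.
- A note adds that "Baseline is the average of the Screening and Baseline visit ALT measurements".

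SAP 3.3.7 instead takes the last value before first dose as Baseline. No table in SAP Section 10 counts subjects who met a Table 8 row or shows ALT and bilirubin together.

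**The concern.** In NASH, raised transaminases at entry are expected, so a liver-safety table has to separate disease at entry from change on treatment. A fixed limit cannot do that alone. Subjects above it before the first dose can add events in every arm, which dilutes a difference between arms. Subjects below it can more than double and still be classed as normal. The protocol already has a Baseline-relative definition, but the analysis plan never counts who met it. Safety and tolerability is a stated secondary objective. If the count is wanted later, someone will have to choose a Baseline and the eligible assessments after the data are known.

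**Working it through.** The plan states no figure here to reproduce; the check compares thresholds.

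**Inputs.** SAP 5.3.2: ALT limit 123, AST limit 102. Protocol 3.3.2: entry ALT below 5 x ULN, AST up to 5 x ULN. Protocol Table 8: 2 x ULN, 2 x Baseline or 300 U/L, and 5 x ULN.

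**Assumed ULN.** The enzyme limits all divide by 3 into whole numbers: 123/3 = 41, 102/3 = 34, 348/3 = 116, 156/3 = 52, 114/3 = 38. They look like 3 x ULN, so I use ALT ULN 41 and AST ULN 34 as working assumptions.

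**Above the limit at entry.** ALT: 5 x 41 = 205, so 124 to 204 is eligible and already abnormal. AST: 5 x 34 = 170, so values above 102 and up to 170 are too. Such a band exists when 5 x ULN exceeds the limit: ALT ULN above 123/5 = 24.6, AST ULN above 102/5 = 20.4.

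**Rises meeting the 2x ALT trigger, at ULN 41:**

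| Baseline ALT | Trigger | Fixed limit (123) | Normal/abnormal shift | Low/normal/high shift |
|---|---|---|---|---|
| Up to 41 | >82 | 83–123 not flagged | None up to 123 | Normal to high |
| 42–61 | >84 to >122 | Not flagged up to 123 | None up to 123 | High to high |
| 62–123 | >124 to >246 | Flagged | Normal to abnormal | High to high |
| 124–204 | >248, capped at >300 | Flagged, as at entry | Abnormal to abnormal | High to high |

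Either shift table shows a change only if the rise is present at Week 18 or the last visit.

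Examples: 50 to 101 exceeds 2 x 50 = 100 but stays below 123. 130 to 290 exceeds 2 x 130 = 260 but starts and ends above 123. Neither moves category in either table. Baselines of 62 to 123 are not part of this gap.

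**Dependence on the ULN.** The unflagged band for a normal Baseline runs from 2 x ULN to 123: 60 to 123 at ULN 30, 100 to 123 at ULN 50, and nothing from ULN 123/2 = 61.5 upward. The unflagged doubling from an elevated Baseline needs a Baseline between the ULN and 61.5, so it ends at the same point. Both problems therefore exist for ALT ULN between 24.6 and 61.5. The particular examples are narrower: 50 counts as elevated only if ULN is below 50, and 130 is an eligible entry value only if ULN is above 130/5 = 26.

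**The 5x row.** At ULN 41 a normal Baseline needs ALT above 205. An elevated Baseline needs more than 5 x a value above 41, or above 500. Every such value exceeds 123 whenever ULN is above 24.6.

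**Which Baseline.** With Screening ALT 45 and Baseline-visit ALT 55, Table 8's Baseline is (45 + 55)/2 = 50 and the SAP's is 55. A later ALT of 101 exceeds 2 x 50 = 100 but not 2 x 55 = 110. The choice can change who counts.

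**The case against.** The strongest reply is that the limits are one display among several. SAP 5.3.2 also plans change from Baseline by time point, two shift tables referenced to Baseline, and listings of all values. SAP 5.2.5 adds Baseline-adjusted analyses of ALT and AST, and SAP 5.3.1 a summary of liver-specific adverse events. Table 8 is a monitoring tool, and neither document promises to tabulate it. The Medical Monitor and the DSMB also review safety.

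Much of this stands. A reader might infer that the whole safety analysis ignores Baseline, or that every Table 8 signal is reported as normal. The documents do not support that. The normal/abnormal shift table separates subjects already abnormal at entry, and the low/normal/high table shows a normal-Baseline rise that persists to Week 18 or last visit. Nor are the more serious rows simply lost. The 5x row is always flagged in the ULN range above. In the row combining ALT and bilirubin, total bilirubin above 2.00 mg/dL may itself be flagged, depending on its ULN. The symptomatic row involves symptoms that can be reported as adverse events.

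What the reply does not reach is the per-arm count. Group changes do not count subjects over a trigger, and an average fall in ALT, which is also an efficacy endpoint, can coexist with individual rises. Liver-specific events depend on reporting rather than a laboratory rule, and SAP Section 10 lists no table for them. Listings do not compare arms.

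**Conclusion.** The point holds as a gap in safety reporting at Table 8's 2x level. It is not a contradiction between the documents, because the SAP delivers the shift tables and liver-event summary that Protocol 9.2.5 promises. Two things follow from the fixed limits: Table 14.3.4.4 can count subjects already above a limit at entry, and more than doubling from a mildly elevated Baseline, or from one already above 123, leaves no trace in either shift table.

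The size rests on an assumed ALT ULN of 41; the problem exists from 24.6 to 61.5 U/L. The documents give no distribution of Baseline ALT, so the number of subjects affected cannot be estimated. The entry problem applies to ALT and AST and possibly to ALP and GGT, which have no specific entry limit. It does not generally apply to total bilirubin, INR or HbA1c, which eligibility restricts.

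A reader might also infer that the direct bilirubin limit (0.20 mg/dL) is an error because it is a tenth of the total bilirubin limit. Without a laboratory ULN, the documents do not show that.

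**What to change.** - Keep the fixed limits, described as descriptive.
- State that Table 14.3.4.4 counts only post-dose, treatment-emergent abnormalities, and define that term for a subject already above a limit before dosing.
- Add one table: the number of subjects per arm meeting each ALT/bilirubin row of Protocol Table 8 at any post-dose assessment, including unscheduled ones, using Table 8's own Baseline (the mean of the Screening and Baseline-visit ALT).

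The laboratory data are already collected, and no clinical rule changes. The cost is modest extra programming: a second ALT Baseline alongside SAP 3.3.7, to be labelled clearly; the separate bilirubin condition for Gilbert's syndrome; and inclusion of unscheduled retests, which SAP 3.3.6 assigns to a visit only when they fall within its listed windows.
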